# 2 Methods

### 2.1 Intervention

A detailed description of the intervention is provided in section 5 of the protocol. Briefly, the intervention includes access to an online web platform with 12 modules (SWiM sessions) consisting of psychoeducational content, reflective exercises, and behavioural experiments, to be completed weekly. After participants had completed session 4, they received a telephone call from their SWiM Coach. The coach also sent a tailored email at week 10.

### 2.2 Control

The wait-list control group received standard advice in the form of a leaflet from the European Association for the Study of Obesity (EASO) on diet, physical activity, and mood during the COVID 19 pandemic, tailored to people living with obesity. After completing 4-month follow-up assessments, participants in the standard advice group were provided access to SWiM-C.

### 2.3 Trial design

This is a randomised, parallel two-group trial. Participants were randomised to either the SWIM-C intervention or to a standard advice wait list control. Participants completed quantitative outcome assessments online at baseline, at 4 months and at 12 months.

### 2.4 Randomisation

See section 4.2 in the study protocol.

### 2.5 Sample size

We recruited 388 participants (192 in intervention, 196 in standard advice). Details are provided in the consort flow diagram (Figure 1).

### 2.6 Framework

We will adopt a superiority hypothesis testing framework, testing whether the SWiM-C intervention is superior to current standard advice for people with overweight and obesity (standard advice from the European Association for the Study of Obesity (EASO) on diet, physical activity and mood during the COVID 19 pandemic) at 12-month follow-up.

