5.2 Control Intervention

Participants who are randomised to the control arm will receive standard advice from the European Association for the Study of Obesity (EASO) on diet, physical activity and mood during the COVID 19 pandemic.(6) They will also be wait-listed to receive access to the SWiM website after the study ends.

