7.2 Outcome Assessments

All outcomes will be assessed via online self-report questionnaires. Participants will be asked to weigh themselves on the day that they complete the outcome assessment so that they can report a self-measured weight. At 12 months, intervention and control participants will complete the intervention engagement questionnaire, since control participants received access to the SWiM website after the 4-month follow-up. This will allow us to control for intervention engagement in analyses, and to compare intervention experiences between intervention participants who received the website in conjunction with support by a coach, and control participants who received only the website without coach support.

Participants will complete a demographics questionnaire at baseline based on Progress-Plus(16) factors.

The study coordination team will send email/phone reminders to participants if a questionnaire has not been completed after 7 days.

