8.3 Cost-effectiveness analysis

A cost-effectiveness analysis (CEA) will be undertaken, comparing the incremental costs and effects of the SWiM programme (i.e. acceptance-based weight maintenance) versus standard care.

The outcomes used in the cost-effectiveness analysis will be the change in weight over time and the health-related quality of life (HRQOL), which will be expressed in Quality Adjusted Life Years (QALYs). Although the current value set for the 5 levels version of the EuroQol EQ-5D questionnaire (EQ-5D-5L) suffer from low quality and reliability issues, we anticipate that these problems will be solved by the time the analysis will be performed. (17) In the absence of high-quality and reliable value set for the EQ-5D-5L, the analyses will be conducted using the cross-walk algorithm developed by van Hout et al as conform with the NICE position statement. (17,18)

Missing data in outcomes is anticipated, and it will be handled using multiple imputation methods.

The imputed mean cost and mean effectiveness in each arm will be used to obtain an incremental cost-effectiveness ratio (ICER), which is calculated by dividing the mean cost difference by the mean effectiveness difference. These mean differences will be ascertained by using regression methods and will be adjusted by the prespecified subgroups accordingly to the statistical analysis plan.

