# **3** Statistical principles

### 3.1 Confidence intervals and p-values

95% confidence intervals will be calculated around relevant estimates of effect.

**Multiplicity**: As we have specified a single primary endpoint (weight change from baseline to 12 months) to test the effectiveness of the intervention (confirmatory analysis), adjustments for multiple endpoints are unnecessary (1). All other outcome measures are secondary and therefore subsidiary and exploratory (1,2). P-values will only be reported for the main effects and interaction analyses of the primary outcome; 95% confidence intervals will be reported for all outcomes/comparisons.

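### The SAP names standard advice as the 12-month comparator, but controls were offered the SWiM website from month 4, so a null result or the effect size at 12 months does not describe SWiM-C against standard advice alone

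*SAP*

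**What the plan says.** **Hypothesis.** SAP 2.6 describes a superiority test at 12-month follow-up, "testing whether the SWiM-C intervention is superior to current standard advice for people with overweight and obesity", and identifies that advice as the EASO material. The last line of SAP 1.1 and the primary objective in SAP 1.2 name the same comparator. So does the secondary objective on weight change from 4 to 12 months. SAP 3.1 calls this the "single primary endpoint (weight change from baseline to 12 months) to test the effectiveness of the intervention" and labels the analysis confirmatory.

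**What controls received.** SAP 2.2: "After completing 4-month follow-up assessments, participants in the standard advice group were provided access to SWiM-C". Protocol 7.2 agrees on timing ("control participants received access to the SWiM website after the 4-month follow-up") and describes "control participants who received only the website without coach support". Protocol 5.2 differs: "They will also be wait-listed to receive access to the SWiM website after the study ends".

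**Analysis.** SAP 3.3 analyses people as randomised, whatever their adherence. The primary model in SAP 5.2 has terms for group, timepoint, their interaction, baseline weight and the stratifiers. It has no term for engagement. Protocol 8.1 says that the 12-month analyses must account for control-arm use of SWiM and requires engagement as a covariate. SAP 5.5 lists only the move to a random-intercepts model as a deviation.

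**Handling of control uptake.** SAP 3.2 will report how many controls reached 1, 4, 8 and 12 sessions. SAP 5.2 adds two per-protocol analyses: intervention participants with at least 4, or at least 8, sessions against controls with fewer than 4.

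**The concern.** The confirmatory claim and the randomised contrast do not match. For the last 8 of the 12 months, the control policy includes an offer of the web component of the programme under test. A small or absent 12-month difference could then mean that SWiM-C does no better than advice, or that some controls gained part of the benefit, and the as-randomised estimate cannot tell these apart. The 4-to-12-month secondary objective is more exposed, because control access opens at the start of that window.

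A null is a realistic prospect. SAP 1.1 reports that the 4-month data, collected before control access opened, were compatible with no effect on weight. The SAP does not say how a 12-month null would be interpreted.

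**Working it through.** **1. What the 12-month coefficient compares**

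| Period | Intervention arm | Control arm |
|---|---|---|
| Baseline to month 4 | SWiM-C with coach | Standard advice |
| Month 4 to month 12 | Follow-up after SWiM-C | Offer of website, no coach |

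Analysed as randomised, the group coefficient at 12 months compares these two whole sequences. Of the two follow-up points, only month 4 compares SWiM-C with standard advice alone.

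**2. Reproducing the planned sample size (protocol 8.2)**

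Inputs: difference 1 kg, SD 6 kg, correlation 0.9, 90% power, 5% level (taken as two-sided), 20% dropout.

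- Residual SD after baseline adjustment: 6 × √(1 − 0.9²) = 2.615 kg.
- n per arm: 2 × (1.960 + 1.282)² × 2.615² / 1² ≈ 143.7, rounded up to 144.
- With dropout: 144 / 0.8 = 180 per arm, 360 in total. This matches the protocol.

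The calculation is for baseline to 4 months. Neither document gives power at 12 months.

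**3. Illustration of dilution**

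Let u be the share of controls who use SWiM and f the fraction of the full effect that they gain. Neither is in the documents, so both are assumed. The 4-month planning figures are also assumed to hold at 12 months.

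- Observed difference = 1 kg × (1 − u × f).
- Standard error with 144 per arm: 2.615 × √(2/144) = 0.308 kg, so 1 kg is 3.245 standard errors.
- Power = Φ(3.245 × difference − 1.96).

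The last column uses the recruited 192 and 196 less 20% dropout (153.6 and 156.8). The standard error is 2.615 × √(1/153.6 + 1/156.8) = 0.297 kg.

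| u | f | Difference (kg) | Power, 144 per arm | Power, recruited N |
|---|---|---|---|---|
| 0 | – | 1.00 | Φ(1.285) = 90% | 92% |
| 0.1 | 0.5 | 0.95 | Φ(1.123) = 87% | 89% |
| 0.5 | 0.5 | 0.75 | Φ(0.474) = 68% | 71% |
| 0.3 | 1 | 0.70 | Φ(0.311) = 62% | 65% |
| 0.5 | 1 | 0.50 | Φ(−0.338) = 37% | 39% |

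If the correlation with 12-month weight were 0.8 instead of 0.9 (also an assumption), power at the recruited N would be 69% with no uptake and 45% at u = 0.5, f = 0.5.

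**4. Do the planned safeguards restore the named comparison?**

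- Uptake counts show how far dilution is possible. They do not change what is estimated.
- The per-protocol analyses select people on engagement after randomisation, so the groups are no longer protected by randomisation. Controls with 1 to 3 sessions still count as not engaged.
- The protocol's engagement covariate is also measured after randomisation. Restoring it would not give an unbiased estimate of SWiM-C against advice alone.

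**The case against.** The strongest reply is that the plan is open about the access and partly handles it. The design is labelled a wait-list trial, uptake will be tabulated, two per-protocol analyses are specified, and the 4-month contrast is already reported. As-randomised analysis is a legitimate treatment-policy comparison. All of this stands. What it leaves untouched is the hypothesis, which still names a comparator that the control arm did not have throughout.

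A reader might infer three stronger things that the documents do not support.

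- *That superiority cannot be tested at 12 months.* If SWiM has no effect in either form, delayed access adds no difference and the type I error is kept. If web access does not worsen weight, it can only shrink a benefit, so a significant benefit would still support superiority.
- *That a null will be misreported.* No passage says so. The SAP is silent on interpretation, which is a gap and not a stated intention.
- *That a 12-month cost-effectiveness ratio is diluted.* Protocol 8.3 plans an analysis "comparing the incremental costs and effects of the SWiM programme (i.e. acceptance-based weight maintenance) versus standard care" but gives no time horizon, and the SAP contains no economic analysis. The point applies only if the horizon runs past month 4.

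The loss may also be small. Controls were offered a website without a coach, and low uptake would cost little, as the 10% row shows.

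**Conclusion.** The mismatch is documented and affects the trial's single confirmatory claim, so the comparator should be restated. The 12-month estimate is a valid randomised comparison, but of immediate coach-supported SWiM-C with advice followed by an offer of unsupported web access. A null, or the size of the effect, cannot be attributed to SWiM-C against standard advice alone.

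The size is a range and not an estimate. In the illustrated scenarios with uptake, power runs from 87% down to 37% with 144 per arm, against 90% with none. This rests on assumed uptake, on web users gaining between none and all of the full effect, and on 4-month planning inputs carried to 12 months.

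Two documentary faults stand whatever the uptake: the passages on when controls get access contradict each other, and the engagement covariate required by protocol 8.1 was dropped without being listed. SAP 5.5 explains its changes by a protocol written for 4 months only, but the protocol supplied covers the 12-month analysis and specifies that covariate.

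**What to change.** - In SAP 1.1 (last line), 1.2 (including the 4-to-12-month secondary objective) and 2.6, restate the comparison as immediate coach-supported SWiM-C against standard advice for 4 months followed by the offer of unsupported SWiM-C web access. Name it a treatment-policy estimand and leave the primary model unchanged.
- Add that only the 4-month contrast estimates SWiM-C against standard advice alone, and that a null 12-month difference will not be read as no effect against standard advice.
- In SAP 5.5, list the omission of the engagement covariate, with the reason. Do not restore it as a remedy, because it is measured after randomisation.
- Reconcile protocol 5.2 with protocol 7.2, protocol 8.1 and SAP 2.2 on when controls receive access.
- If the economic analysis in protocol 8.3 extends beyond month 4, describe its comparator in the same way.

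The cost is wording only: no new data and no change to the analysis population or the primary model. The downside is a narrower 12-month claim.

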### 2.7 Measures

The following measures were assessed:

- Self-reported weight (kg)
- Patient Health Questionnaire 8-item (PHQ-8)
- Generalized Anxiety Disorder 7-item (GAD-7) scale
- Perceived Stress Scale (PSS-4)
- Acceptance and Action Questionnaire Weight Related (Revised) (AAQW-R)
- Three-Factor Eating Questionnaire (TFEQ-R21)
- International Physical Activity Questionnaire (IPAQ)
- Health related quality of life and wellbeing (EQ-5D-L ; ICECAP-A )
- Demographics
- Website Usage (data analytics)
- Intervention adherence (number of sessions and coach calls completed)

(For details and references, see section 6 in the study protocol)

### 2.8 Timing of outcome assessments

Time points for assessments of the different measures are shown in Table 1.

TIMEPOINT	0 (baseline)	4 months	12 months
Height	Х		
Weight	Х	Х	Х
Demographics	Х		
Mental	Х	Х	Х
wellbeing			
(depression,			
anxiety,			
stress)			
Psychological	Х	Х	Х
flexibility			
Eating	Х	Х	Х
Behaviour			
Physical	Х	Х	Х
Activity			
Quality of Life	Х	Х	Х
/Wellbeing			
Intervention		Х	Х
Engagement			
Adherence to		Х	Х
intervention			

#### Table 1. Schedule of assessments.

### 2.9 Interim analyses and stopping guidance

No interim analyses are planned for this study.

### 2.10 Timing of final analysis

All statistical analyses will be undertaken following completion of the study (when the database is closed for 12 month follow up data).

# **3** Statistical principles

### 3.1 Confidence intervals and p-values

95% confidence intervals will be calculated around relevant estimates of effect.

**Multiplicity**: As we have specified a single primary endpoint (weight change from baseline to 12 months) to test the effectiveness of the intervention (confirmatory analysis), adjustments for multiple endpoints are unnecessary (1). All other outcome measures are secondary and therefore subsidiary and exploratory (1,2). P-values will only be reported for the main effects and interaction analyses of the primary outcome; 95% confidence intervals will be reported for all outcomes/comparisons.

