2. AIMS AND OBJECTIVES

2.1 Aim

To evaluate the effect of the SWiM intervention on weight, eating behaviour, physical activity and wellbeing compared to current standard advice for people with overweight and obesity. Primary Objective

To evaluate the effect of SWiM on weight at 4 months and 12 months follow-up, compared to standard advice on diet, physical activity and mood.

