6. OUTCOMES AND MEASURES

6.1 Primary Outcome

Self-reported weight at 4 months.

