8. STATISTICS AND QUANTITATIVE DATA ANALYSIS

8.1 Statistical analysis

A detailed statistical analysis plan will be developed and signed off by the Trial Steering Committee (TSC) prior to analysis. Participants will be analysed in the group to which they were randomised, based on the intention-to-treat principle. The primary analysis will estimate the baseline-adjusted difference between intervention groups in change in weight from baseline to 4 months, using a linear regression model including randomisation group, baseline weight, and the randomisation stratifiers (sex, BMI classification). Participants with missing values of weight at 4 months will be excluded (ie, a complete-case analysis which assumes outcome data are missing at random conditional on covariates in the model). If there are >5% of participants with missing values of weight, a sensitivity analysis will be performed using multiple imputation by chained equations – this makes the missing at random assumption but provides increased precision compared with a complete-case analysis. Linear regression will be used to estimate the baseline-adjusted difference between intervention groups in change in weight from baseline to 12 months and 4 months to 12 months. Since the control group was waitlisted and therefore received access to the SWiM website after the 4-month follow-up, analyses at 12 months will need to account for intervention usage in the control group. Regression models for the 12-month follow-up will therefore include intervention engagement (as measured using the intervention engagement questionnaire and/or website analytics) as a covariate. Full details of this analysis will be provided in the statistical analysis plan. Continuous secondary outcomes will be analysed using the same method.

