# 1 Introduction

### 1.1 Trial background and rationale

The social distancing and isolation measures imposed during the COVID-19 pandemic beginning March 2020, including the closure or reduced operating of some weight management programmes and services, mean that adults with overweight and obesity in the UK are at increasing vulnerability to weight gain, and associated negative impacts on physical health and mental wellbeing. There is good evidence that interventions based on acceptance and commitment therapy (ACT) are effective for weight management and may improve mental wellbeing and psychological determinants of weight control.(4) However, acceptance-based programmes are usually psychologist-led and the cost and scarcity of psychologists specialising in obesity mean it is not possible to support everyone who would benefit from this type of intervention.

We developed a supported self-help intervention (SWiM-C; Supporting Weight Management during COVID 19) that aims to help adults with overweight and obesity to manage their weight and eating behaviour, be more physically active, and protect their emotional wellbeing during the COVID pandemic. The 12-week intervention is based on ACT, targets known psychological determinants of weight management and is delivered via an online platform with remote support from a guide or coach.

If the SWiM-C intervention proves to be effective it could be rolled out on a larger scale to support people in situations involving high levels of stress, reduced access to resources, and/or low levels of mobility.

We previously evaluated the effect of SWiM-C on bodyweight in adults with overweight and obesity at 4 months post intervention compared to standard advice (written materials giving advice on diet, physical activity and mental health during the COVID-19 pandemic). The data were compatible with no effect of the intervention on bodyweight, physical activity, mental health, or emotional eating. The intervention improved psychological determinants known to lead to successful weight management in the longer term (uncontrolled eating, cognitive restraint, and experiential avoidance) and had a protective effect on wellbeing.

The current study compares the effectiveness of SWiM-C with standard advice at 12 months post intervention.

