### 5 Analysis

### 5.1 Outcome definitions

### **Primary Outcome**

Change in self-reported weight from baseline to 12-month follow-up (kg).

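### After the 4-month result was reported, the SAP labels 12-month weight change the sole confirmatory primary endpoint; its no-adjustment rationale does not hold for the trial as a whole, and the change of timepoint is not listed as a deviation

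*SAP*

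**What the plan says.** **Protocol.** Section 6.1 lists one primary outcome: "Self-reported weight at 4 months". Section 8.1 agrees: "The primary analysis will estimate the baseline-adjusted difference between intervention groups in change in weight from baseline to 4 months". Section 8.2 powers the trial on a 1 kg difference in change to 4 months. The primary objective, printed under section 2.1, is wider: "To evaluate the effect of SWiM on weight at 4 months and 12 months follow-up". Section 8.1 also plans a regression for change in weight to 12 months. The protocol gives no split of alpha between the two timepoints and no testing order.

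**SAP.** The revision history runs from 19/01/2022 to 16/03/2022. Section 1.1 reports the 4-month comparison as already done: "The data were compatible with no effect of the intervention on bodyweight". Section 1.2 puts the primary objective at 12 months, and section 5.1 defines the primary outcome as change in weight to 12 months. Section 3.1 gives the reasoning, "As we have specified a single primary endpoint (weight change from baseline to 12 months) to test the effectiveness of the intervention", labels this the confirmatory analysis, concludes that "adjustments for multiple endpoints are unnecessary", and reserves p-values for the primary outcome. Section 5.2 sets the 4-month contrast aside because it has been reported. Section 5.5 lists one deviation, the move from linear regression to a random intercepts model. It explains this by saying that the protocol predates the decision to add a 12-month follow-up.

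**The concern.** The argument in SAP 3.1 is sound for a trial with one primary endpoint. This trial already had a primary outcome at another timepoint, the one it was powered on, and its result was known when the SAP was written. The SAP draws no consequence from that in 3.1 and does not list the changed timepoint in 5.5.

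What is at stake is the claim that a 12-month p-value below 0.05 would support. Under the present wording it could be presented as confirming effectiveness, with no reference to the earlier primary test in the same randomised participants.

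**Working it through.** **1. Which endpoint was the trial sized for?** Inputs from protocol 8.2: difference 1 kg, SD 6 kg, correlation 0.9, 5% level (taken as two-sided), 90% power, 20% dropout.

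- Residual SD after adjusting for baseline: 6 × √(1 − 0.9²) = 2.615 kg.
- Per arm: 2 × (1.960 + 1.282)² × 2.615² / 1² = 143.7, so 144.
- With dropout: 144 / 0.8 = 180 per arm, 360 in total.

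The planned 360 is reproduced exactly, for the 4-month outcome. Neither document states power or a sample size for 12 months.

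**2. Error rate across the two tests.** Let Z4 and Z12 be the test statistics for weight at 4 and 12 months, each tested two-sided at 5%. With no true effect at either time, the chance of at least one false positive is 1 − P(|Z4| < 1.96 and |Z12| < 1.96). If the tests were independent this would be 1 − 0.95² = 9.75%. The documents do not give the correlation, so a range is assumed, using a bivariate normal distribution:

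| Correlation | At least one false positive | 12-month false positive, given a non-significant 4-month test |
|---|---|---|
| 0.3 | 9.5% | 4.75% |
| 0.5 | 9.1% | 4.3% |
| 0.7 | 8.35% | 3.5% |
| 0.8 | 7.8% | 3.0% |
| 0.9 | 7.0% | 2.1% |

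The last column is (second column − 5%) / 95%. If all three weights correlate at 0.9 (an assumption; the protocol gives 0.9 for repeated measures generally), the correlation given baseline is (0.9 − 0.81) / (1 − 0.81) = 0.47 and the trial-level rate is 9.15%. Counting only false positives in favour of SWiM-C, the rate is 3.5% to 4.8% for correlations of 0.9 to 0.3, against 2.5% for one test.

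**3. What would a plan for two primary timepoints have looked like?** With 2.5% for each test (Bonferroni), the trial-level rate is at most 4.9%. Power for 1 kg with 144 analysed per arm falls from 90% to 84.2%, if the same SD and correlation apply. With a fixed sequence of 4 months then 12 months, a non-significant first test leaves no alpha for a confirmatory second. Neither scheme is in the protocol.

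**4. What 5.5 says against the protocol.** SAP 5.5 says that only a 4-month follow-up was planned when the protocol was written. The protocol supplied includes 12 months in its primary objective, in section 3, in the schedule in 7.1 and in the analysis in 8.1. The two statements need reconciling, most simply by naming the protocol version meant.

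**The case against.** Several points on the other side are good, and they limit what can be claimed.

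- **Twelve-month weight is not new.** It is in the protocol's primary objective, and a 12-month regression is planned. This stands, and the 12-month analysis itself is legitimate. It does not rescue the wording of SAP 3.1: if both timepoints are primary, there is no single primary endpoint, and if only 6.1 counts, the primary timepoint is 4 months.
- **The two tests are not of the same hypothesis.** A reader might infer that one question is asked twice. Controls were given SWiM-C website access after the 4-month assessment (SAP 2.2; protocol 7.2), so the 12-month contrast is earlier coached access against later uncoached access. The outcome is shared; the treatment contrast is not.
- **The 12-month test keeps its own 5% level.** This is correct. If the 4-month test was non-significant, the table shows that the chance of a false positive at 12 months is below 5%. The inflation belongs to the pair of tests, that is, to a claim of effectiveness made for the trial.
- **Nothing is hidden.** A reader might take SAP 2.9, "No interim analyses are planned for this study", and the timing statement in 2.10 to imply that no comparison by arm had been made. SAP 1.1, 3.2 and 5.2 all say that the 4-month assessment had been reported. What remains is that 2.10 speaks of all analyses when it can only mean those at 12 months.

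**Conclusion.** The point holds as a fault of labelling and disclosure. The claim that no adjustment is needed because there is one primary endpoint does not fit a trial whose powered primary outcome, at another timepoint, had already been tested and reported. The trial-level false-positive chance is about 7.0% to 9.5%, assuming two-sided 5% tests, approximate normality and a correlation of 0.9 down to 0.3.

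A reader might go further and infer that 12 months was made primary because the 4-month result was disappointing. The documents do not support that. They show that the confirmatory label appears in a SAP that already reports the 4-month result; they do not date the decision to add or promote the 12-month timepoint. Nor do they say that the 4-month effect was zero, only that the data were compatible with none.

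No estimate, model or confidence interval changes. What changes is what may be concluded from a 12-month p-value below 0.05.

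**What to change.** In the SAP:

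- **1.2, 3.1, 5.1 and 5.2:** label 12-month weight change a secondary, longer-term outcome, and state that the trial's primary outcome is 4-month weight (protocol 6.1), already reported. In 5.2 this includes the primary-outcome heading and the per-protocol text that refers to the primary outcome analysis.
- **3.1:** delete the single-endpoint, confirmatory and no-adjustment wording. Report the 12-month effect with its 95% CI. Rewrite the rule on p-values as well; otherwise relabelling leaves this SAP with none. Any 12-month p-value should be described as non-confirmatory.
- **5.5:** record the change of timepoint from 4 to 12 months, with its date and reason. Reconcile it with the protocol's primary objective and with the statement that only a 4-month follow-up was planned.
- **2.10:** say that the analyses meant are those at 12 months, and that a comparative 4-month analysis came first.

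If the team wishes to keep 12 months as primary, the minimum is to declare it in 5.5 as a change made after the 4-month result and to qualify 3.1 accordingly.

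The cost is wording, including a reconciliation with the protocol's primary objective; no new data or modelling is needed. The downside is that a positive 12-month result can no longer be called confirmatory.
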